4.2. Discussion of Study Design, Including the Choice of Control Groups

Participants were randomized to receive either Sing 2016 M2SR H3N2 or placebo within each cohort. Participants received one or two doses depending upon the cohort into which they enrolled. The targeted number of participants randomized to receive either vaccine or placebo are given below ([Table 2](#)).

4.3. Selection of Study Population

The study population consists of male and female pediatric volunteers aged 6 months to 18 years, inclusive, and generally in good health. Participants 2-17 years should be “non-naïve,” having been vaccinated against seasonal influenza in a prior season. Inclusion and exclusion criteria are presented in Sections 5.1 and 5.2 of the protocol, respectively.

4.4. Statistical Considerations for the Study Design

4.4.1. Sample Size Considerations

The probability of observing one or more safety events, such as a reactogenicity event or an adverse event of a particular classification, for varying sample sizes, given underlying true event probabilities is presented below ([Table 3](#)).

Among the 25 participants in each of Cohorts 1-2 considered for the safety reviews prior to enrolling the subsequent cohorts, there is a 22.2% chance of observing at least one uncommon event and a 92.8% chance of observing at least one common event (bolded and underlined in [Table 3](#)).

The primary objective of this study is to determine the safety and tolerability of the Sing2016 M2SR H3N2 influenza vaccine, which will be assessed via the incidence of adverse events of different types. While the study was not designed to achieve a pre-determined level of precision, confidence intervals (CIs) will be estimated for some of the binary endpoints. The exact 95% Clopper-Pearson CIs that would result from observing varying numbers of events in groups of possible interest is presented below ([Table 4](#)).

For illustration, if zero events of a certain type were observed in an individual vaccine group or in Cohorts 3-4 aggregate vaccine groups after one dose with N=30 participants, true event probabilities above 11.6% could be ruled out at the $\alpha=0.025$ level, compared to 2.8% in the combined vaccine groups (N=132). Binomial CIs are widest at 50% events observed (the estimates associated with approximately [or exactly] 50% observed events are bolded in [Table 4](#)). Within an individual vaccine group or in Cohorts 3-4 aggregate vaccine groups after one dose with N=30 participants, the maximum half-width for a 95% CI would be 18.7%, compared to 10.7% across active vaccine groups in Cohorts 1-4. In the case of substantial loss to follow-up or missed visits, these estimates give an idea of the loss of precision due to decreasing the effective sample size.

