The first two groups to be vaccinated will be Cohorts 1 and 2. Cohort 1 consists of 45 children 9–17 years old. Thirty of them will receive one dose of the vaccine at a dose of 10^9 TCID₅₀, and 15 will receive one dose of placebo. Cohort 2 comprises 45 children 2–8 years old. Thirty of them will receive one dose of the vaccine at a dose of 10^8 TCID₅₀ and 15 will receive one dose of placebo. Sites will enroll participants into Cohorts 1 and 2 simultaneously. Once 25 or more participants in each of the first 2 cohorts (Cohorts 1 and 2) have completed Day 8, the SRC will evaluate if any halting rules are met and if it is deemed safe, enrollment in Cohort 3 may open. Enrollment within each cohort will not halt during the SRC review. Cohort 2 must fully enroll before enrollment in Cohort 3 may begin. If any halting rules are met or if the SRC raises any safety concerns other than halting rules that should be independently reviewed, the external Safety Monitoring Committee (SMC) will meet to discuss the data prior to progression to the next cohort.

Cohort 3 consists of 25 children 2–8 years old. Fifteen of them will receive one dose of vaccine at 10^9 TCID₅₀ and 10 will receive one dose of placebo. Once all 25 participants in Cohort 3 have completed Day 8 of follow-up, similar to Cohorts 1 and 2, the SRC will review to ensure no

halting rules are met and if no rules are met and the SRC determines it is safe to proceed, simultaneous enrollment into Cohorts 4 and 5 can begin. If any halting rules are met or any concerns are raised by the SRC, an external SMC may meet to discuss the data for recommendations on either progression or clinical trial modification before progression to the next cohort.

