4. STUDY DESIGN

4.1 Overall Design

This is a Phase 1b, randomized, double-blind, dose-escalating, age de-escalating, placebo-controlled study of 200 children 6 months through 17 years of age, inclusive, who are in good health and meet all eligibility criteria. To allow for simultaneous enrollment at the four research sites, the number of children in each cohort and the total number of children in the entire study may slightly deviate from the targeted numbers mentioned throughout the protocol.

The study design includes 7 cohorts in Protocol Versions 1-4. Given a number of non-safety-related contingencies (timelines, budgets, recruiting, and lack of additional vaccine lots), Cohorts 5, 6, and 7 will no longer be enrolled as of Protocol Version 5.0. Cohorts 5, 6, and 7 included children 6 to 23 months old. The study-related objectives and endpoints have been updated to reflect that only Cohorts 1 through 4, were enrolled. Descriptions of Cohorts 5, 6, and 7 have not been removed from the remainder of the protocol design.

All participants in Cohorts 1, 2, 3, and 4, will be “non-naïve”, having been vaccinated against seasonal influenza in a prior season. Cohorts 5, 6, and 7 will be 6 to 23 month-olds who are influenza-naïve (no previous influenza vaccine and no previous documented influenza infection).

A cohort of 45 healthy children 9-17 years old (Cohort 1) will receive a single dose of vaccine at the 10^9 TCID₅₀ dose of the Sing2016 M2SR H3N2 vaccine or placebo. At the same time, the second cohort (Cohort 2) will begin enrollment.

Cohort 2 will consist of 45 healthy children 2-8 years old who will also receive a single dose of the vaccine, but they will be given at 10^8 TCID₅₀ or placebo. Once there is sufficient evidence of safety and tolerability in Cohorts 1 and 2 and enrollment has completed of all 45 in each of these cohorts, the third cohort (Cohort 3) will begin enrollment.

Cohort 3 will consist of 25 healthy children 2-8 years old who will receive a single dose of the 10^9 TCID₅₀ dose of vaccine or placebo. Once there is sufficient evidence of safety and tolerability in Cohort 3 and enrollment has completed for this cohort, the fourth and fifth cohorts (Cohorts 4 and 5) will begin enrollment.

Cohort 4 will consist of 25 healthy children 2-8 years old who will receive 2 doses of the 10^9 TCID₅₀ dose of vaccine or placebo. Participants in Cohort 4 will enroll concurrently with participants in Cohort 5.

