10. TECHNICAL DETAILS

SAS version 9.4 or above, or R version 4.3.2 or above, will be used to generate all tables, figures and listings.

**11. SUMMARY OF CHANGES IN THE CONDUCT OF THE STUDY OR
PLANNED ANALYSES**

Due to the limited availability of study product and funding to support additional years of enrollment into Cohorts 5, 6, and 7, the decision was made to stop enrollment after the final participant was enrolled into Cohort 4. This modification is reflected in protocol version 5.0. As such, results in the CSR will be provided only for Cohorts 1-4.

For descriptive analyses, continuous variables will not be summarized by first and third quartiles.

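### SAP 4.4.1 and Protocol 9.2 say zero events would rule out rates above 2.8% in the pooled vaccine groups, but N=132 counts 42 vaccinees in cohorts that were not enrolled; for Cohorts 1-4 the bound is 4.0%

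*SAP*

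**What the plan says.** SAP 4.4.1 introduces its Table 4 as showing "The exact 95% Clopper-Pearson CIs that would result from observing varying numbers of events in groups of possible interest". It then works through one case. "if zero events of a certain type were observed" in a group of 30, "true event probabilities above 11.6% could be ruled out at the $\alpha=0.025$ level", "compared to 2.8% in the combined vaccine groups (N=132"). Protocol 9.2 has the same sentence under its Table 6.

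Both documents also say that the youngest cohorts do not exist. Protocol 4.1 states that "Cohorts 5, 6, and 7 will no longer be enrolled as of Protocol Version 5.0". SAP 4.1 says enrollment stopped after the last Cohort 4 participant, and SAP Section 11 says that "results in the CSR will be provided only for Cohorts 1-4".

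The matching row is already printed. SAP Table 4 and Protocol Table 6 each have a line for any vaccine in Cohorts 1-4, N=90, where zero events gives an interval of 0 to 4%. Later in the same SAP paragraph, the largest half-width for pooled vaccinees is given as 10.7%, and there it is explicitly tied to Cohorts 1-4.

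**The concern.** The paragraph uses two denominators for pooled vaccine recipients: 132 for the zero-event bound and 90 for the half-width. Only the second describes the trial that was run.

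Safety is the primary objective, and each primary endpoint is defined both by cohort and across Cohorts 1-4. The SAP plans tables for all vaccine recipients covering AESIs, SAEs and NOCMCs (Tables 57, 65 and 73). These are event types for which zero or few events is a plausible result, and the zero-event bound is what a reader would apply to them. The N=132 row is labelled only as any vaccine, so it could easily be matched to those tables.

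SAP Tables 3 and 4 sit in the mock-up appendix, and the SAP Preface describes the sample tables as planned for the final analyses. A figure left uncorrected there could pass into the clinical study report, where it would overstate what a clean safety result excludes in children.

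**Working it through.** **Inputs**

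- Method: exact Clopper-Pearson, two-sided 95%, so 0.025 in the upper tail (SAP 4.4.1).
- Events observed: 0 (SAP 4.4.1).
- Planned vaccine recipients by cohort (Protocol Table 2, SAP Table 2): Cohort 1, 30; Cohort 2, 30; Cohort 3, 15; Cohort 4, 15; Cohort 5, 6; Cohort 6, 18; Cohort 7, 18. For the two largest groups the protocol synopsis says "Thirty of them will receive one dose of the vaccine at a dose of 10^9 TCID₅₀" (Cohort 1) and "Thirty of them will receive one dose of the vaccine at a dose of 10^8 TCID₅₀" (Cohort 2).

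**Step 1: where 132 comes from**

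- Cohorts 1-7: 30 + 30 + 15 + 15 + 6 + 18 + 18 = 132.
- Cohorts 5-7: 6 + 18 + 18 = 42.
- Cohorts 1-4: 132 − 42 = 90.

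**Step 2: reproduce the stated figures**

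With zero events the Clopper-Pearson upper limit is 1 − 0.025^(1/N).

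- N=30: 1 − 0.025^(1/30) = 11.57%, stated as 11.6%.
- N=132: 1 − 0.025^(1/132) = 2.756%, stated as 2.8%.

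Both reproduce. A one-sided 0.05 limit at N=132 would be 2.24%, which does not match, so the 0.025 reading is the right one.

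**Step 3: the same formula for the cohorts that were enrolled**

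- N=90: 1 − 0.025^(1/90) = 4.016%, or 4.0%. This agrees with the printed N=90 row.
- Ratio of bounds: 4.016 / 2.756 = 1.46.

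**Step 4: what 2.8% would mean with 90 vaccinees**

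If the true rate were 2.8%, the chance of seeing no events in 90 children would be 0.972^90 = 7.8%, about three times the 2.5% implied by the stated alpha level. A bound of exactly 2.8% needs ln(0.025)/ln(0.972) ≈ 129.9, that is 130 vaccinees.

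**Step 5: sensitivity to enrollment**

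Both documents allow actual numbers to differ slightly from target. The documents given do not state the enrolled number, so a range is assumed:

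| Vaccine recipients, Cohorts 1-4 | Upper limit with 0 events |
|---|---|
| 85 (assumed) | 4.25% |
| 90 (target) | 4.02% |
| 95 (assumed) | 3.81% |

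No small deviation from target brings the bound near 2.8%.

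**The case against.** The best defence is that nothing depends on this sentence. It is offered as an illustration. Protocol 9.1 says the study was not designed for any set level of power or precision, and SAP 4.4.1 says the same about precision. No population, halting rule, interim decision or analysis uses 132, and the reported intervals will be computed from the data for Cohorts 1-4. All of that stands, and it limits the severity.

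A second defence is that the correct figure is already in the tables, and that Protocol 4.1 discloses that descriptions of Cohorts 5-7 were left in the design text. This explains the leftover in the protocol. It does not cover the SAP. Protocol Version 5.0 is dated December 2023, while SAP 2.1 refers to a submission made in May 2024. The SAP was therefore completed after the cancellation, yet it carried the sentence over with no caveat at that point, and its Section 11 does not mention the precision statement.

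A reader might go further and infer that all the pooled precision statements are out of date. The documents do not support that:

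- The half-width in the text is 10.7%, already correct for Cohorts 1-4. The 8.8 points that 132 would give is stated nowhere and can only be derived from the N=132 row.
- The chances of seeing at least one event at true rates of 1% and 0.1% (73.5% and 12.4% at N=132; 59.5% and 8.6% at N=90) are entries in separately labelled table rows. Each is correct for its own N, and no sentence claims the higher pair for this trial. The detection probabilities highlighted in the text, 22.2% and 92.8%, refer to N=25.

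**Conclusion.** The point holds for one stated figure. The zero-event bound for pooled vaccinees should be 4.0%, not 2.8%, because 42 of the 132 vaccinees behind it were never enrolled. The arithmetic is right for N=132, and the denominator is out of date.

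The conclusion rests on the target of 90 vaccine recipients in Cohorts 1-4. It is not sensitive to modest departures from that target (3.8% to 4.25% over an assumed 85 to 95).

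A reader might infer that the safety analysis itself, or the trial's ability to meet its primary objective, is compromised. It is not: no planned analysis or decision changes, and no reported estimate will use 132. Severity is minor to moderate, as a correction to a stated precision figure that should be made before the sample-size text is reused in the study report.

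**What to change.** In SAP 4.4.1, replace the comparison figure with 4.0% for the combined vaccine groups of Cohorts 1-4 (N=90). Make the same change in Protocol 9.2 if the protocol is amended again. A protocol amendment needs IRB approval (Protocol 10.1), and this point alone hardly justifies one after enrollment has ended.

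In SAP Tables 3 and 4, and in Protocol Tables 5 and 6 on the same condition, delete three rows or mark them as not enrolled. The N=8 and N=18 rows describe only Cohorts 5-7. The N=132 row should say that it includes cohorts that were not enrolled.

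The half-width sentence needs no change. The cost is one sentence and three rows in each of two tables per document, using a number already printed there. The price is a less favourable stated bound.

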4.4.2. Allocation of Subjects to Study Arms (Randomization)

Enrollment of participants was done online using the enrollment module of the Electronic Data Capture (EDC), maintained by the Statistical and Data Management Coordinating Center (SDMCC). Randomization to receive either Sing2016 M2SR H3N2 vaccine or saline placebo within each cohort was conducted via a randomization scheme that was stratified by site. Participants were assigned to receive either Sing2016 M2SR H3N2 vaccine or saline placebo at Day 1 (and Day 29, if applicable) after providing consent and confirmation of eligibility with the study inclusion and exclusion criteria.

4.5. Study Products

4.5.1. Study Products Administered

Participants in Cohorts 1-3 were administered 1 mL of Sing2016 M2SR H3N2 (diluted to the target dosing concentration) or placebo delivered intranasally via a disposable polypropylene syringes (Henke-Ject) with each syringe fitted with a MAD300™ nasal device (MAD300; *Teleflex, Morrisville, NC, USA*) on Day 1. Remaining participants received two vaccinations, one at Day 1 and one at Day 29, administered as noted above.

4.5.2. Identity of Investigational Product(s)

4.5.2.1. Product 1: Sing2016 M2SR H3N2 Intranasal Influenza Vaccine

The Sing2016 M2SR vaccine is provided as a frozen liquid formulation in 2 mL cryovials. Each vial contains ~0.6 mL of vaccine formulated to contain infectious viral particles of Sing2016 M2SR encoding the HA and NA of influenza virus strain A/Singapore/INFIMH-16-0019/2016 (H3N2). The virus is suspended in Sucrose Phosphate Glutamate with Sodium Chloride (SPG-NaCl) buffer comprised of 10% sucrose, 5 mM glutamic acid, 136.9 mM sodium chloride, 2.67 mM potassium chloride, 1.47 mM potassium dihydride phosphate and 8.1 mM disodium phosphate, at pH 7.2. The Sing2016 M2SR vaccine is clear to opalescent, colorless to slightly yellow suspension.

4.5.2.2. Product 2: SPG buffer to be used as the diluent for Product 1

The vaccine diluent, SPG-NaCl buffer (10% sucrose, 5 mM glutamic acid, 136.9 mM sodium chloride, 2.67 mM potassium chloride, 1.47 mM potassium dihydride phosphate and 8.1 mM disodium phosphate, at pH 7.2), is provided as a frozen, liquid formulation. It is a clear, colorless solution that is used to prepare dilutions of the investigational vaccine for the lower dose treatments.

4.5.2.3. Product 3: Placebo

The placebo consists of a commercially prepared 0.9% sodium chloride for injection, USP.

4.5.2.4. Product 4: Seasonal Inactivated Influenza Vaccine (IIV4)

All participants without contraindications will be given injectable IIV4 using a licensed product. All available IIV products licensed for children in the US are now quadrivalent.

4.5.2.5. Product 5: MAD300™ Sprayer Device

The intranasal delivery device, i.e., nasal spray device, is comprised of a MAD300™ mucosal atomization device and a 1 mL Henke-Ject (low dead space) syringe. The MAD300™ is made from radiation-stable medical-grade polycarbonate material and is compliant with USP Class VI and ISO 10993 requirements. It is manufactured by Teleflex Medical and is a conical shaped component with a Luer-lock feature for attachment to the filled syringe. For intranasal administration of the Sing2016 M2SR vaccine and placebo, the MAD300™ conical shape forms a plug in the nostril and rapid depression of the syringe plunger atomizes the liquid as it passes through the device nozzle into a fine mist.

4.5.3. Selection of Doses in the Study

Depending on the cohort, participants were randomized to receive either one or two doses of either Sing 2016 M2SR H3N2 (ranging from 10^7 TCID₅₀ to 10^9 TCID₅₀) or placebo. Justification for selection of these doses can be found in Section 4.3 of the protocol.

4.5.4. Selection and Timing of Dose for Each Subject

On Day 1, eligibility was reviewed. Participants in Cohorts 1-3 received Sing 2016 M2SR H3N2 or placebo intranasally on Day 1 if all eligibility criteria were met. All remaining participants received Sing 2016 M2SR H3N2 or placebo intranasally on Day 1 and Day 29 if eligibility were met on the day of vaccination.

4.5.5. Blinding

An unblinded interim immunogenicity analysis was performed (further details can be found in [Section 5.6.1](#)). These analyses were made available to the pharmaceutical partner for planning for future studies, with no public dissemination of results, and not used to make any decisions concerning the conduct of the trial. The SAP was finalized prior to unblinding of individual participants for the pharmaceutical partner and PI.

4.5.6. Prior and Concomitant Therapy

Details of prior and concomitant therapy can be found in Section 6.5 of the protocol.

4.5.7. Study Product Compliance

Participants were directly observed at the time of dosing by a member of the clinical research team who is licensed to administer the study product.

4.6. Efficacy, Immunogenicity, and Safety Variables

4.6.1. Safety Variables

Safety is assessed by the incidence, frequency, and severity of:

1. Solicited local reactogenicity events in the 7 days following administration of each dose of vaccine.
2. Solicited systemic reactogenicity events in the 7 days following administration of each dose of vaccine.
3. Unsolicited non-serious adverse events in the 28 days following administration of each dose of vaccine.
4. Adverse events of special interest (AESIs) from the time of first vaccination through the end of the study (in the month of April of the calendar year following enrollment)
5. Serious adverse events (SAEs) from the time of first vaccination through the end of the study (in the month of April of the calendar year following enrollment)
6. New-onset chronic medical conditions (NOCMCs) from the time of first vaccination through the end of the study (in the month of April of the calendar year following enrollment)

Additional details for data contributing to safety variables, including definitions, can be found in the protocol (Sections 8.3 and 8.4)

4.6.2. Immunogenicity Variables

Hemagglutination inhibition (HAI) and microneutralization (MN) antibody results as measured in serum will be reported by the research laboratory at Duke University. HAI, MN antibody titers and neuraminidase inhibition (NAI) titers as measured in plasma will be reported by the laboratory at VisMederi. Assay results for HAI and MN, as measured in serum and plasma, and NAI as measured in plasma, are reported as endpoint titers, with values of 10^*2^k , where $k=0, 1, 2, \text{ etc.}$, or are reported to be below the lower limit of detection (LOD). Antigen specific non-dilution adjusted ECL signals, dilution factors, and total sIgA concentrations, as measured by BAMA, will be reported by the research laboratory at Duke University. sIgA titers and total sIgA concentrations, as measured by ELISA, will be reported by the laboratory at FluGen, Inc. See [Section 3.3](#) for definitions of derived variables for immunologic data.

All immunogenicity data will be uploaded into the SDMCC's electronic data capture system. Data for the remaining exploratory assays and corresponding analyses not covered in this document will be described in a separate analysis plan addendum(a).

5. GENERAL STATISTICAL CONSIDERATIONS

5.1. General Principles

For screening and baseline visits, the last assessment value obtained prior to the first vaccination/dose of study product will be used. If participants completed assessments at both scheduled and supplementary visits, the assessments from the scheduled visit will be considered in the statistical analyses, tabular summaries, and figures. However, if an assessment is completed only at supplementary visits, then the assessment from the earliest supplementary visit occurring after the scheduled visit will be included in the statistical analyses, tabular summaries, and figures. Results of all assessments, including those performed during supplementary visits, will be included in the listings.

Generally, summaries will be presented by cohort and vaccination group (i.e., 9-17 yrs, 10^9 TCID₅₀ Sing2016 M2SR, 1 Dose; 9-17 yrs, Placebo, 1 Dose; 2-8 yrs, 10^8 TCID₅₀ Sing2016 M2SR, 1 Dose; etc., called “analysis group” throughout the SAP). Post-first dose safety results for participants in Cohorts 3 and 4 receiving active vaccine may be combined as both cohorts receive the same dose and belong to the same age group.

For descriptive analyses, continuous variables will be summarized by the non-missing sample size, mean, standard deviation (SD), and the minimum, median, and maximum. Categorical variables will be summarized by frequencies and percentages of observed levels, based on the non-missing sample size. When calculating incidence, or any sub-classification thereof (e.g., by study vaccination, time period, severity, relatedness, etc.) each participant will only be counted once at the maximum value of the respective variable (e.g., maximum severity, maximum relatedness, etc.), and any repetitions will be ignored. All tables will be annotated with the analysis population and the total population size relevant to that table, including any missing observations. Data listings will typically be sorted by cohort (even if not presented), vaccination group, site, participant, and visit number within participant, where appropriate.

For continuous variables, CIs will be computed based on the t-distribution, unless the data appear especially non-normal and the sample sizes for the analysis are insufficient to apply the central limit theorem. Bootstrap CIs may be calculated instead if the t-distribution is determined to be unsuitable. For binary variables, CIs will be computed using the exact Clopper-Pearson method.

For safety endpoints, summaries may also include a column for all participants receiving active study vaccination and all participants receiving placebo.

Subgroup analyses will be performed on a conditional basis for immunogenicity endpoints, as outlined in [Section 7.2](#). Subgroups include age, dose level, sex, clinical site, prior receipt of IIV4, time between prior receipt of IIV4 and study vaccination, prior receipt of COVID-19 vaccination, time between prior receipt of COVID-19 vaccination and study vaccination, and seroprotection.

